3.2.2 SECONDARY

OBJECTIVES	ENDPOINTS	JUSTIFICATION FOR ENDPOINTS
Secondary		

OBJECTIVES	ENDPOINTS	JUSTIFICATION FOR ENDPOINTS

 • To compare, between the same two groups over the same time period, 
 1) The rate of self-reported new episodes of respiratory illness (URI or ILI), DIA and UFI. 2) The rate of self-reported new episodes of 
 a) ILI b) URI c) DIA d) UFI 3) The rate of clinically-confirmed episodes of the study syndromes 4) The rate of laboratory-confirmed episodes of the study syndromes • First event, per protocol analysis (receipt of all 3 doses) and extended per protocol analysis (receipt of at least one dose) of primary endpoint and secondary endpoints 1-7 (primary analyses will focus on all events and intention-to-treat analyses). • Sub-group analyses for potential effect measure modification of Primary Endpoint and Secondary Endpoints 1-7 by 
 1) Sex (males or females) 2) Season (spring = January cohorts; summer = May cohorts; winter = September cohorts) 	
 1. Number of self-reported new episodes of respiratory illness (URI or ILI), DIA and UFI. 2. Number of self-reported new episodes of URI 3. Number of self-reported new episodes of ILI 4. Number of self-reported new episode of DIA 5. Number of self-reported new episodes of UFI 6. Number of clinically-confirmed episodes of the study syndromes, defined as an episode resulting in a visit to the RUSVM Student Health Services with a recorded ICD10 of J00 (acute nasopharyngitis); J11 (influenza due to unidentified influenza virus); R19.7 (diarrhea) or R50.9 (fever, unspecified). 7. Number of laboratory-confirmed episodes of the study syndromes, defined as clinically-confirmed episodes with laboratory diagnosis of influenza virus, respiratory syncytial virus or metapneumovirus (URI/ILI episodes) or rotavirus or norovirus (DIA episodes) . 	
For Secondary Endpoint 1, in any week a single participant could report one of the following:
 
 • No CID episode • One CID episode (URI or ILI or DIA or UFI) • Two CID episodes (either URI or ILI, and DIA) 
By this definition, a participant cannot experience more than two CID episodes within a week, as occurrence of URI together with ILI is considered an episode of ILI only, and occurrence of URI, ILI and/or DIA precludes the occurrence of UFI.
 
We also will attempt to determine impact on etiologically confirmed outcomes but we expect few episodes to meet this criteria and thus study power will be low. Etiological confirmation will be done for a limited range of pathogens only (influenza virus, respiratory syncytial virus, metapneumovirus, rotavirus and norovirus) through an independent research protocol (RUSVM IRB protocol #17-11-FL) and the test results sent back to the RUSVM Student Health Services.

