
OBJECTIVES	ENDPOINTS	JUSTIFICATION FOR ENDPOINTS

3) Class (new arrivals [VP and 1st semester] vs. 5th semester)
 
 Subset analyses of Primary Endpoint and Secondary Endpoints 1-7 in the subset of participants excluding those participants categorized as immunosuppressed (reporting use of immunosuppressive medications or treatments or occurrence of immunosuppressive medical conditions in baseline questionnaire) 		

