3.2.3 TERTIARY

OBJECTIVES	ENDPOINTS	JUSTIFICATION FOR ENDPOINTS
Tertiary/Exploratory		

 Among the vaccinated group only, to compare Primary Endpoint and Secondary Endpoints 1-7 between high responders and low responders, defined by RVNA titers measured by rapid fluorescent foci inhibition test (RFFIT) at day 180 after first vaccination. Explore latency period and duration of effect on Primary Endpoint and Secondary Endpoints 1-5. Explore the effect of dose (1 vs. 2 vs. 3) on Primary 	
 Primary Endpoint and Secondary Endpoints 1-7 Primary Endpoint and Secondary Endpoints 1-5 Primary Endpoint and Secondary Endpoints 1-5 	See above

OBJECTIVES	ENDPOINTS	JUSTIFICATION FOR ENDPOINTS
Endpoint and Secondary Endpoints 1-5.		

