12 DATA COLLECTION METHODS

After enrollment, participants will complete a questionnaire that will capture data on relevant baseline characteristics including sex, age, health and vaccination status. (Baseline CRF; Appendix C). Participants will complete a short survey each week, starting in study week 3, to capture self-reported episodes of illness (respiratory, diarrheal and febrile illness; Primary Endpoint and Secondary Endpoints 1-5) in the preceding week (Appendix G). Surveys will be sent by email to all participants each Monday. Participants who have not completed the survey by Wednesday afternoon will be sent a request by email to complete the survey for the preceding week. Surveys will be sent weekly, for 26 weeks. A participant is considered to have completed the study one week after receipt of the final (26th) weekly survey for that participant's cohort.

As an incentive to enhance participant retention and response rates in weekly illness surveys, all participants who complete a weekly survey will be entered into a draw each week for a chance to win a EC\$25 gift voucher to a food/beverage vendor on the RUSVM campus. Selection of a winner each week will be done by computer-generated random sampling. The weekly winner will be notified by email in the week following the draw.

Clinically- and laboratory-confirmed episodes of study syndromes (Secondary Endpoints 6 & 7) will be collected by study personnel at RUSVM Student Health Services, as part of the

routine clinic visits and diagnostics. At the end of each 26-week observation period for each study cohort, data from that cohort will be compiled by the director of the RUSVM Student Health Services, anonymized to protect privacy and aggregated by study arm, before being sent to the Data Analyst who will conduct the analysis.

Occurrence of expected Adverse Events (Safety Endpoint 1) will be solicited in an online survey (Appendix H) sent to participants 3 days after receiving an injection (for dose 1, 2 and 3). Occurrence of unsolicited adverse events and serious adverse events (Safety Endpoint 2) will be captured by study personnel at RUSVM Student Health Services through completion of an Adverse Event form (Appendix I; See **Section 15.3, Identification of Adverse Events** for details).

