14 STATISTICAL METHODS

The analysis of the primary endpoint and secondary endpoints 1-7 will be conducted after all randomized participants have completed the study (one week after receipt of the final weekly survey) or have withdrawn from the study, whichever occurs first. Primary analysis will be based on intention-to-treat analysis of all events (that is, not just occurrence of first events). The comparison of incidence rates of CID episodes (primary endpoint and secondary endpoints 1-7) between the treatment arms will be performed using a negative binomial regression model, which accounts for different lengths of observation period. Participants' number of CID episodes will be modelled as a function of treatment group, with the number of weeks of observation included as an offset in the model. This analytic model estimates the rate ratio, λ_t / λ_c , which quantifies the risk of CID episodes associated with rabies vaccination (λ_t) in comparison to placebo injection (λ_c). Statistical significance will be controlled at the 2-sided, 0.05 alpha level, and the estimated rate ratio compared with 1, assuming the following statistical hypothesis:

H_0 (null hypothesis): Rate ratio = 1

H_1 (alternative hypothesis) Rate ratio $\neq 1$

Treatment effect will be based on the coefficient in the model. Statistical significance at the pre-specified alpha level will be based on a Wald testing procedure. CID rates (primary

endpoint and secondary endpoints 1-7) for rabies vaccine and placebo, and the rate ratio, will be presented and will include 95% confidence intervals.

A detailed description of the statistical methods that will be used for the primary and secondary endpoints will be provided in a Statistical Analysis Plan (SAP).

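### Section 12 sends Endpoint 6 and 7 data to the analyst aggregated by study arm, which cannot feed the participant-level model in Section 14 or the linked analyses in Section 3.2

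*Combined protocol and SAP*

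**What the plan says.** Section 12 has Student Health Services collect Secondary Endpoints 6 and 7. After each cohort's 26-week period its director compiles them, and the data are "anonymized to protect privacy and aggregated by study arm, before being sent to the Data Analyst who will conduct the analysis".

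Section 14 states one model for all the illness endpoints: the comparison of rates ("primary endpoint and secondary endpoints 1-7) between the treatment arms will be performed using a negative binomial regression model". In that model each participant's "number of CID episodes will be modelled as a function of treatment group, with the number of weeks of observation included as an offset". Significance comes from a two-sided Wald test at 0.05.

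Section 3.2 carries Endpoints 6 and 7 into further analyses:
- Section 3.2.2: "First event, per protocol analysis (receipt of all 3 doses) and extended per protocol analysis (receipt of at least one dose"), for the primary endpoint and Endpoints 1-7.
- Section 3.2.2: "Sub-group analyses for potential effect measure modification of Primary Endpoint and Secondary Endpoints 1-7 by" sex, season and class.
- Section 3.2.2: "Subset analyses of Primary Endpoint and Secondary Endpoints 1-7 in the subset of participants excluding those participants categorized as immunosuppressed".
- Section 3.2.3: "Among the vaccinated group only, to compare Primary Endpoint and Secondary Endpoints 1-7 between high responders and low responders", with response defined by the day-180 titer.

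The comparison of one, two or three doses in Section 3.2.3 stops at Endpoint 5, so it is not part of this point.

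**The concern.** The data route and the analysis use different units. Section 14 needs one count and one observation time per participant; Section 12 supplies totals by arm for each cohort. A negative binomial model takes its dispersion from the spread of counts between participants, and a total does not show that spread. Anonymized totals also cannot be joined to a titer, a baseline answer or a dose record.

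Endpoints 6 and 7 are the only illness endpoints that do not rest on the weekly self-report. In a trial where only participants are described as blinded and the primary outcome is self-reported symptoms, they are the natural corroboration. If Section 12 is followed as written, either the method or the data transfer will have to be changed from what the protocol states.

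**Working it through.** **1. The plan's own figure.** Section 8 gives a control rate of 2 over 26 weeks, rate ratio 0.75, participation 0.8 of the period, k = 0.4, two-sided alpha 0.05 and power 0.8. The negative binomial formula with true rates is

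n per arm = (1.960 + 0.842)² × [(1/0.8)(1/2 + 1/1.5) + 2 × 0.4] / (ln 0.75)² = 214.18, rounded up to 215.

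The total is 430, as stated. It concerns the primary endpoint only and does not depend on how Endpoints 6 and 7 are transferred.

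**2. Do arm totals determine the Section 14 result?** No rate is given for Endpoints 6 and 7, so the primary-endpoint figures serve as an illustration. The control total is 215 × 2 × 0.8 = 344 episodes and the vaccine total is 344 × 0.75 = 258, with 21 weeks for every participant. These totals were spread over participants in three simulated ways, and the Section 14 model was fitted to each. With equal follow-up,

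SE(log RR) = √(1/344 + 1/258 + 2k/215), z = ln 0.75 / SE, ln 0.75 = −0.2877.

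| Fitted k | Rate ratio | SE(log RR) | Wald p |
|---|---|---|---|
| 0.28 | 0.750 | 0.097 | 0.003 |
| 0.94 | 0.750 | 0.125 | 0.021 |
| 2.11 | 0.750 | 0.163 | 0.077 |
| Poisson on totals (k = 0) | 0.750 | 0.082 | 0.0005 |

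The totals are identical in every row. They fix the rate ratio and leave the SE, interval and p-value open.

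**3. Cost of a Poisson test on the totals.** Suppose a participant's count has mean μ and variance μ + kμ². The true variance is then 1 + kμ times the Poisson variance, so a nominal 5% test has size 2[1 − Φ(1.96/√(1 + kμ))].

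| μ | k | 1 + kμ | Size | Simulated (215 per arm, 20,000 runs) |
|---|---|---|---|---|
| 0.1 | 0.4 | 1.04 | 5.5% | 4.8% |
| 0.5 | 0.4 | 1.20 | 7.4% | 7.2% |
| 0.1 | 2 | 1.20 | 7.4% | 7.0% |
| 0.5 | 2 | 2.00 | 16.6% | 16.5% |

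The value k = 0.4 is the plan's figure for the primary endpoint. The means and k = 2 are assumptions.

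**4. Which further analyses have a route?**
- *Titer.* Section 13 sends titers to the PI or Study Coordinator. The contrast lies wholly within the vaccine arm, so an arm total says nothing about it.
- *Immune status.* It is defined from the baseline questionnaire. Section 10 has clinic staff check that form at Visit 1, after which the PI stores it. The clinic therefore sees the information, but no step attaches it to the Endpoint 6 and 7 data.
- *Sex, class, per-protocol, first event.* Each needs totals split further, or participant rows. Section 12 states neither.
- *Season.* Data are compiled by cohort, so a crude comparison by season is possible.

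**The case against.** Several points on the other side have weight.

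- *Section 13 says research data carry a study identification number.* That is a general rule. Section 12 is specific to these two endpoints and describes anonymized, aggregated data. At the least the two sections need reconciling.
- *Aggregated could mean participant rows sorted by arm.* The text does not describe such a file. If it did, and the rows carried observation weeks, the main model could be fitted, but anonymized rows still could not be joined to titer or baseline status.
- *Section 21 gives the PI and Study Coordinator the full dataset.* Section 12 names the Data Analyst as the person who does the analysis, and no section gives that person participant-level rows for these endpoints.
- *Section 14 leaves detail to a SAP.* A SAP could name a method suited to totals. It could not fit the Section 14 model to rows that are never delivered.
- *The stakes are modest.* This stands. For etiologically confirmed outcomes Section 3.2.2 says "we expect few episodes to meet this criteria and thus study power will be low", and with rare events the size inflation is at the low end of the range. The titer analysis is exploratory. Transfers run cohort by cohort while analysis waits for all participants, so the mismatch could be noticed and repaired in time.

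A reader might infer that Endpoints 6 and 7 are lost or that the trial's main result is in doubt. The documents support neither: the clinic holds the source records, and the primary endpoint and Endpoints 1-5 come from participant-level surveys. A reader might also try to quantify wider intervals by estimating overdispersion across arm-by-cohort totals. No section proposes that analysis, and Section 14 has no cohort term, so no such figure belongs here. Nor are these the only endpoints free of self-report: the antibody endpoint in Section 3.2.5 is laboratory-measured. The statement holds for illness endpoints.

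**Conclusion.** The contradiction is real and should be resolved before analysis. With the data route in Section 12, the model that Section 14 prescribes for Endpoints 6 and 7 cannot be fitted. The titer analysis of these endpoints cannot be done, and the non-immunosuppressed analysis has no stated route. The first-event, per-protocol, sex and class analyses depend on splits or rows that are not described. A crude rate ratio by arm, and by season, remains available.

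That totals do not identify the dispersion needs no assumption about event rates. The size range of about 5.5% to 16.6% does: it rests on assumed means of 0.1 to 0.5 and k of 0.4 to 2, and on the choice of a Poisson test, which the plan does not propose. The top of the range needs both assumptions at their upper end.

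**What to change.** Amend Section 12 so that, at the end of each cohort's observation period, Student Health Services sends one record per participant. Each record should carry the study identification number already used in Sections 12 and 13, no name or email, the Endpoint 6 and Endpoint 7 episode counts, and the date of the first episode of each for the first-event analysis. Merge allocation at the final analysis; observation weeks, titer, baseline status and doses received can be joined by the same number. The clinic will need a list of study numbers, since the Visit 1 form as described in Section 11.2 lists name and email but no such number.

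The cost is somewhat less privacy protection than aggregation gives, and keying about 430 records in cohort batches. Section 18 requires a formal amendment with IRB approval. The consent wording must be checked, with a re-consent determination if the form changes. Endpoint 7 test results come through a separate IRB protocol (Section 3.2.2), so its sharing terms need checking too. No extra visits or participants are needed.

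If participant-level transfer is not permitted, keep Section 12 and restrict Sections 3.2 and 14 for Endpoints 6 and 7 to a named crude comparison of arms, stating how overdispersion is handled. This has no privacy cost, but it also needs an amendment and gives up the linked analyses.

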13 DATA MANAGEMENT

Weekly survey data on illness episodes, will be collected through the Qualtrics® platform. Qualtrics safeguards all customer data, and uses secure data centers to ensure the highest protection as per the requirements of the Health Information Technology for Economic and Clinical Health Act (HITECH) (www.qualtrics.com/security-statement/). Survey data will be accessible only by study investigators. Weekly survey data will be downloaded by the data analyst from Qualtrics servers each week. Downloaded data will be stored on a password-protected computer and backed up to an encrypted external hard drive. Study participant research data for purposes of statistical analysis and scientific reporting, will not include the participant's contact or identifying information. Rather, individual participants and their research data will be identified by a unique study identification number. The code for re-identification of study data will be held by the data analyst in a separate password-protected database.

For the vaccine efficacy ancillary study, RFFIT RVNA titers will be sent by the laboratory to the PI or Study Coordinator, who will enter the data in the CRF.

For the immunology ancillary study, laboratory results will be sent by the Immunology Specialist to the PI or Study Coordinator, who will enter the data in the CRF. The Data

Analyst will return a deidentified dataset containing the immunology laboratory results to the Immunology Specialist for further analysis.

14 STATISTICAL METHODS

The analysis of the primary endpoint and secondary endpoints 1-7 will be conducted after all randomized participants have completed the study (one week after receipt of the final weekly survey) or have withdrawn from the study, whichever occurs first. Primary analysis will be based on intention-to-treat analysis of all events (that is, not just occurrence of first events). The comparison of incidence rates of CID episodes (primary endpoint and secondary endpoints 1-7) between the treatment arms will be performed using a negative binomial regression model, which accounts for different lengths of observation period. Participants' number of CID episodes will be modelled as a function of treatment group, with the number of weeks of observation included as an offset in the model. This analytic model estimates the rate ratio, λ_t / λ_c , which quantifies the risk of CID episodes associated with rabies vaccination (λ_t) in comparison to placebo injection (λ_c). Statistical significance will be controlled at the 2-sided, 0.05 alpha level, and the estimated rate ratio compared with 1, assuming the following statistical hypothesis:

H_0 (null hypothesis): Rate ratio = 1

H_1 (alternative hypothesis) Rate ratio $\neq 1$

Treatment effect will be based on the coefficient in the model. Statistical significance at the pre-specified alpha level will be based on a Wald testing procedure. CID rates (primary

endpoint and secondary endpoints 1-7) for rabies vaccine and placebo, and the rate ratio, will be presented and will include 95% confidence intervals.

A detailed description of the statistical methods that will be used for the primary and secondary endpoints will be provided in a Statistical Analysis Plan (SAP).

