8 SAMPLE SIZE

The estimated number of participants needed to achieve the study's primary objective is 430 (215 in each group). The sample size was calculated using the approach for comparing two negative binomial rates based on true rates (Approach 2 in [17]), implemented using the function *power.nb.test* in package 'MKmisc' in R, and assuming the following parameter values:

- Alpha level = 0.05
- Targeted power = 0.8
- Event rate for control group = 2 (expected mean number of new CID episodes [composite primary endpoint] over 26 weeks)
- Rate ratio under alternative hypothesis = 0.75
- Average length of participation (accounting for drop-out and non-response) = 21 weeks (0.8 of 26-week observation period)
- Negative binomial dispersion parameter (k in [17]) = 0.4

The three nuisance parameters (average length of participation, event rate for control group and negative binomial dispersion parameter) were estimated from data collected over 7 weeks of a pilot study of rates of CID episodes in 90 RUSVM students (40 in 1st semester and 50 in 5th semester) from 21 May to 8 July, 2018 (weeks 3 through 9 of summer semester).

An internal pilot study will be done using data from the first 300 participants to complete the study. As the expected enrollment rate is <100 participants per semester, this will allow capture of seasonal variation in event rates (≥ 3 semesters in internal pilot study). The three nuisance parameters will be re-estimated from the internal pilot study data and the sample size recalculated, using a blinded sample size re-estimation method for count data [18, 19], which maintains required power without an increase in the type I error. The sample size will only be increased and not decreased on the basis of the internal pilot study (that is, if the recalculated sample size is smaller than the original sample size, the original sample size will still be used).

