11 ALLOCATION

11.1 SEQUENCE GENERATION

Allocation of participants to study arms will be done by restricted randomization (permuted block design with stratification). Stratification will be by cohort (three cohorts per year: January, May and September) and sex (within cohort). Within strata, randomization will be done by computer-generated randomly permuted blocks of varying size (using the function *blockrand* in the package 'blockrand' in R). Enrolled students will be allocated in a 1:1 ratio to one of the two study arms.

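### The primary model omits the randomization strata (cohort and sex), so any stratum differences in event rate widen the standard error and cost some power or some extra participants

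*Combined protocol and SAP*

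**What the plan says.** Section 11.1 describes permuted blocks within strata: "Stratification will be by cohort (three cohorts per year: January, May and September) and sex (within cohort". Section 14 gives the primary analysis as a negative binomial regression with a two-sided Wald test at the 0.05 level, in which the "number of CID episodes will be modelled as a function of treatment group, with the number of weeks of observation included as an offset". No section adds cohort, sex or any other covariate to that model.

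The plan treats both factors as potentially relevant elsewhere. Section 3.2.2 lists sub-group analyses by sex and by season, with season defined by intake: "Season (spring = January cohorts; summer = May cohorts; winter = September cohorts". Section 8 says of the internal pilot: "As the expected enrollment rate is <100 participants per semester, this will allow capture of seasonal variation in event rates". It also makes the re-estimation one-directional: "The sample size will only be increased and not decreased on the basis of the internal pilot study".

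Section 14 adds that a detailed description of the "statistical methods that will be used for the primary and secondary endpoints will be provided in a Statistical Analysis Plan". The text of that separate plan is not in the document reviewed.

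**The concern.** Stratified randomization makes the arms nearly equal in cohort and sex composition, so differences in illness rate between strata add little to the sampling variability of the log rate ratio. A model without the strata cannot recognise this. It reads those differences as unexplained variation between participants, estimates a larger dispersion, and reports a standard error above the real variability of the estimate.

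The rate ratio is not biased and the false-positive rate is not inflated. What is at stake is efficiency, in one of two forms. Either some power is lost at 430 participants, or the blinded re-estimation sees the larger dispersion and enrols more people to offset variation that the design had already balanced.

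**Working it through.** **Inputs from section 8.** Two-sided alpha 0.05 (sidedness from section 14), power 0.80, control rate 2 per 26 weeks, rate ratio 0.75 (so a vaccine rate of 1.5), average exposure 0.8 of the period, dispersion k = 0.4.

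**Reproducing the plan's figure.** For Approach 2 (true rates):

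- V = (1/0.8)(1/2 + 1/1.5) + 2k = 1.458 + 0.8 = 2.258
- n per arm = (1.96 + 0.8416)² × V / (ln 0.75)² = 7.849 × 2.258 / 0.08276 = 214.2, rounded up to 215, so N = 430
- Power at 215 per arm = Φ(0.2877 / √(2.258/215) − 1.96) = Φ(0.847) = 80.2%

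The stated 430 is reproduced.

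**Adding between-cohort variation.** The planning value of k comes from seven weeks of one summer semester, so it contains no between-cohort variation and is taken here as the within-cohort value. If the log rate varies between cohorts with standard deviation SD, the dispersion seen by a treatment-only model is about 1.4 × exp(SD²) − 1. The documents give no SD, so the values below are assumptions.

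For scale, suppose a sinusoidal yearly pattern averaged over 26-week windows, with three equally spaced intakes a year. The SD is then about ln(peak/trough)/2 × (2/π) × (1/√2), which is 0.09, 0.16 or 0.25 for a peak-to-trough ratio of 1.5, 2 or 3.

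| SD | Treatment-only k | V | n per arm | N for 80% power | Power at 430 |
|---|---|---|---|---|---|
| 0 | 0.400 | 2.258 | 214.2 | 430 | 80.2% |
| 0.1 | 0.414 | 2.286 | 216.8 | 434 | 79.7% |
| 0.16 | 0.436 | 2.331 | 221.1 | 444 | 78.9% |
| 0.2 | 0.457 | 2.373 | 225.01 | 452 | 78.2% |
| 0.3 | 0.532 | 2.522 | 239.2 | 480 | 75.7% |

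**Simulation.** There were 6,000 runs per scenario under rate ratios 0.75 and 1. Each had N = 430 in five cohorts of 86 (fewer than 100 per semester implies at least five), permuted blocks by cohort and sex, within-cohort k = 0.4 and no sex effect. Maximum-likelihood negative binomial models with and without cohort and sex were fitted to the same data.

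| SD | SE, treatment-only / adjusted | Power, treatment-only v adjusted | Gain (points) | Type I error, treatment-only v adjusted |
|---|---|---|---|---|
| 0 | 1.006 | 80.8 v 81.0% | 0.2 | 4.7 v 4.7% |
| 0.1 | 1.010 | 80.6 v 81.3% | 0.7 | 5.1 v 5.4% |
| 0.2 | 1.023 | 78.9 v 80.0% | 1.1 | 5.2 v 5.5% |
| 0.3 | 1.043 | 77.4 v 80.0% | 2.6 | 4.5 v 5.5% |

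The Monte Carlo SE is 0.3 points for the type I error and 0.13 to 0.24 points for the paired power gain. Under rate ratio 0.75 at SD 0.1, 0.2 and 0.3, the treatment-only mean SE against the empirical SD of the estimate was 0.1029 v 0.1018, 0.1046 v 0.1028 and 0.1072 v 0.1040. The adjusted figures were 0.1019 v 0.1018, 0.1023 v 0.1028 and 0.1028 v 0.1036. The treatment-only SE is therefore too wide, and the adjusted SE is close to the truth.

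**Independent checks.** A second simulation (432 participants, six cohorts) included both season and sex differences. At a between-stratum coefficient of variation of 0.19, power was 76.4% treatment-only against 77.6% adjusted. At 0.35 it was 74.4% against 78.7%, with treatment-only type I error of 3.7 to 3.8%. Mean log rate ratios agreed between the models. A third simulation, with 3,600 runs per scenario, found no power loss at SD 0 and gains of about 1.4 and 2.1 points at SD 0.2 and 0.3.

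**The case against.** **The separate SAP may already include the strata.** That is possible. But section 14 already states the model, so in that case the two texts need aligning.

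**The size rests on an assumed variance.** This stands. On the scale above, a twofold seasonal swing gives SD 0.16, power 78.9% and 14 extra participants (444 − 430). SD 0.3 lies beyond even a threefold swing, and with five cohorts the formula overstates its k (about 0.48 in simulation against 0.532). That row is an upper illustration and should not carry the case.

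**The gain is not entirely free.** Adjusted type I error averaged (4.7 + 5.4 + 5.5 + 5.5)/4 = 5.3%, about two Monte Carlo SEs above 5%; the third simulation gave about 5.0 to 5.7%. Fitting more terms slightly underestimates k, so a small part of the apparent gain comes from that. The estimate itself is hardly more precise, since its empirical SDs barely differ between models; what improves is mainly the match of the reported SE to the true variability. This stands as a limit on the claim, and is a reason to use main effects only and to retain the treatment-only fit.

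**Power is already protected by the re-estimation.** True, but that protection is paid for in participants, which is the cost at issue.

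**Some parts are less well tested.** The separate benefit of the sex term was not isolated, and the covariate-adjusted blinded re-estimation was not simulated; the N values come from the formula.

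**Conclusion.** The concern holds as a point of efficiency, not validity. The stated model ignores factors on which the trial is stratified, and its SE is somewhat too wide if event rates differ between strata. For an assumed between-cohort SD of 0.1 to 0.2, the simulated SE excess is about 1 to 2%, adjustment is worth about one point of power, and the alternative is 4 to 22 extra participants by formula. At SD 0.3 these become about 4%, 2.6 points and 50 participants. With no stratum differences there is essentially no gain, and adjustment costs no power.

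These figures assume that k = 0.4 is the within-cohort value. If it is the total dispersion instead, adjustment lifts power above the target: from 80.2% to 80.6%, 82.0% or 84.2% at a between-stratum coefficient of variation of 0.1, 0.2 or 0.3.

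**What to change.** - **Section 14:** add cohort and sex as fixed main effects in the primary negative binomial model. Terms for every cohort-by-sex cell are not needed. Keep the treatment-only model as a sensitivity analysis.
- **Secondary endpoints 1 to 5:** use the same terms where event counts allow, with the rule fixed before unblinding.
- **Endpoints 6 and 7:** leave these out. Section 12 says their data are "anonymized to protect privacy and aggregated by study arm" before they reach the analyst, so individual strata are not available.
- **Section 8:** use the same cohort and sex terms, without arm, when the dispersion is re-estimated blinded. Check the operating characteristics of that step by simulation, since this was not done here.
- **Reporting:** section 14 promises arm-specific rates with confidence intervals, so state how these are obtained from an adjusted model.
- **Alignment:** if the separate SAP already specifies the strata, bring section 14 into line with it.

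The change should be made before the re-estimation, and in any case before unblinding. The cost is one line in section 14, one in the re-estimation text and a short reporting rule. Both variables are recorded at randomization, and the planned N of 430 need not change.
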